6.9. Concomitant and Previous Therapy

Concomitant medications will be coded and descriptively summarized by treatment group in terms of frequencies and percentages using the mITT population.

At screening, previous and current PBC treatments are recorded for each patient. A summary of previous medications used for PBC, including zoster immunization and TB vaccine and medications that are discontinued after screening and before the first dose of study drug, will be prepared using frequency counts and percentages by preferred medication name, with preferred medication names sorted by frequency in the baricitinib 4-mg group. Concomitant therapy will be recorded at each visit and will be classified similarly. An additional summary for previous medications used for PBC will be created containing the reason for discontinuation.

Concomitant therapy for the treatment period is defined as therapy that starts before or during the treatment period and ends during the treatment period or is ongoing (has no end date or ends after the treatment period). Should there be insufficient data to make this comparison (for example, the concomitant therapy stop year is the same as the treatment start year, but the concomitant therapy stop month and day are missing), the medication will be considered as concomitant for the treatment period.

Summaries of previous medications will be provided for the following categories:

- Previous PBC therapies
- Previous PBC therapies including reason for discontinuation

Summaries of concomitant medications will be provided for the following categories:

- Concomitant medications for PBC
- Concomitant medications for non-PBC

6.10. Efficacy Analyses

The general methods used to summarize efficacy data, including the definition of baseline value for assessments are described in Section 6.1.

Efficacy will generally be analyzed from Week 0 to Week 12, and patients will be analyzed according to the investigational product to which they were randomized at Week 0 (Visit 3):

Table JAIV.6.2 includes the descriptions and derivations of the primary and secondary efficacy outcomes.

Table JAIV.6.3 provides the detailed analyses including analysis type, method and imputation, population, time point, and comparisons for efficacy analyses.

Table JAIV.6.2. Description and Derivation of Primary and Secondary Efficacy Outcomes

Measure	Description	Variable	Derivation / Comment	Definition of Missing
Alkaline Phosphatase (ALP)	Laboratory measurement of the enzymatic (catalytic) activity of ALP enzyme within the blood.	
 Change from baseline in ALP 	Change from baseline: observed ALP – baseline ALP	Missing if baseline or observed value is missing.
Total Bilirubin and Alkaline Phosphatase (ALP)	Measurement of concentration of total bilirubin in the blood and measurement of the enzymatic (catalytic) activity of ALP enzyme within the blood.	
 Proportion of patients with ALP <1.67 x ULN (and at least 15% decrease from baseline) and total bilirubin < ULN 	If observed ALP < 1.67 x ULN and $\frac{\text{baseline ALP} - \text{observed ALP}}{\text{baseline ALP}} \times 100 \geq 15$, and observed total bilirubin < ULN then conclude that the patient has ALP <1.67 x ULN (and at least 15% decrease from baseline) and total bilirubin < ULN.	Missing if any one of baseline ALP, observed ALP, or observed total bilirubin is missing.

Table JAIV.6.3. Description of Primary and Secondary Efficacy Analyses

Measure	Variable	Analysis Method (Section 6.1.3)	Population (Section 6.1.1)	Comparison/Time Point	Analysis Type
Alkaline Phosphatase (ALP) and Total Bilirubin	• Change from baseline in ALP	MMRM	mITT	Bari 4-mg vs PBO; Week 12	Primary analysis
				Bari 2-mg vs PBO; Week 12	Secondary analysis
	• Proportion of patients with ALP <1.67 x ULN (and at least 15% decrease from baseline) and total bilirubin <ULN at Week 12	ANCOVA using LOCF	mITT	Bari 4-mg vs PBO; Week 12	Supplementary analysis
				Bari 2-mg vs PBO; Week 12	Supplementary analysis
		Logistic regression using LOCF	mITT	Bari 4-mg vs PBO; Week 12	Secondary analysis
				Bari 2-mg vs PBO; Week 12	Secondary analysis
Logistic regression using NRI	mITT	Bari 4-mg vs PBO; Week 12	Supplementary analysis		
		Bari 2-mg vs PBO; Week 12	Supplementary analysis		

Abbreviations: ANCOVA = analysis of covariance; Bari = baricitinib; mITT = modified intent-to-treat; LOCF = last observation carried forward; MMRM = mixed model repeated measures; NRI = nonresponder imputation; PBO = placebo.

6.10.1. Primary Outcome and Methodology

The primary efficacy assessment in Study JAIV will be change in ALP at Week 12. The primary analysis of the study is to test the hypothesis that baricitinib 4-mg is superior to placebo for PBC disease based on the mITT population. MMRM described in Section 6.3.2 will be the primary method of analysis. The treatment difference along with the p-value and 90% confidence intervals will be reported.

6.10.2. Secondary Efficacy Analyses

There will be no adjustment for multiple comparisons for Study JAIV. The secondary efficacy analyses are detailed in Table JAIV.6.3. Health outcome analyses are described in Section 6.11.

6.10.3. Supplementary Analyses

Supplementary analyses for select outcomes have been previously described and include the following:

- Non-responder imputation (NRI) (Section 6.3.3) for categorical secondary outcomes.
- Analysis of continuous outcomes with ANCOVA (Section 6.1.3), with missing data imputed using LOCF (Section 6.3.1) for continuous primary and secondary outcomes.

6.11. Health Outcomes/Quality-of-Life Analyses

The general methods used to summarize health outcomes and quality-of-life measures, including the definition of baseline value for assessments, are described in Section 6.1.

Health outcomes and quality-of-life measures will generally be analyzed according to the formats discussed in Section 6.10.

Table JAIV.6.4 includes the descriptions and derivations of the health outcomes and quality-of-life measures.

Table JAIV.6.5 provides the detailed analyses including analysis type, method and imputation, population, time point, and comparisons for health outcomes and quality-of-life measures.

Table JAIV.6.4. Description and Derivation of Health Outcomes and Quality-of-Life Measures

Measure	Description	Variable	Derivation / Comment	Definition of Missing
Itch Numeric Rating Scale (NRS)	The Itch NRS is a patient administered, 11 point horizontal scale anchored at 0 and 10, with 0 representing “no itch” and 10 representing “worst itch imaginable.” Overall severity of a patient’s itching is indicated by selecting the number that describes the worst level of itching in the past 7 days.	
 Change from baseline in Itch NRS 	Change from baseline: observed Itch score – baseline Itch score	Missing if baseline or observed value is missing.
Fatigue Numeric Rating Scale (NRS)	The Fatigue NRS is a single item, patient administered, 11 point horizontal scale anchored at 0 and 10, with 0 representing “no fatigue” and 10 representing “as bad as you can imagine.” Overall severity of a patient’s fatigue is indicated by selecting the number that describes the worst level of fatigue during the past 7 days.	
 Change from baseline in Fatigue NRS 	Change from baseline: observed Fatigue score – baseline Fatigue score	Missing if baseline or observed value is missing.
Functional Assessment of Chronic Illness Therapy Fatigue (FACIT-F)	The FACIT-F measures an individual’s self-reported level of fatigue during their usual daily activities over the past 7 days. The scale is composed of 13 items measured on a 4-point Likert scale (4 = very much to 0 = not at all). The total score ranges from 0 to 52, and higher scores represent less fatigue. A score of less than 30 indicates severe fatigue (Webster et al. 2003).	
 Change from baseline in FACIT-F total score 	Change from baseline: observed FACIT-F total score – baseline FACIT-F total score according to version 4 of the scoring guidelines. (http://www.ser.es/wp-content/uploads/2015/03/FACIT-F_INDICE.pdf) Individual item scoring will be done for exploratory purposes.	Missing individual items within the questionnaire are acceptable as long as more than 50% of the items are answered, e.g. 7 of 13. If less than 7 items are answered baseline or observed value is missing.

Measure	Description	Variable	Derivation / Comment	Definition of Missing
Quality of Life for Primary Biliary Cirrhosis (PBC-40)	The PBC-40 is a disease-specific, 40-item, patient-reported survey containing 6 domains: overall symptoms, itch, fatigue, cognition, social, and emotional. Response options for overall symptoms, itch, fatigue, and cognition are on a 5-point scale: “Never,” “Rarely,” “Sometimes,” “Most of the time,” and “Always.” Response options are also on a 5-point scale for social and emotional: “Not at all,” “A little,” “Somewhat,” “Quite a bit,” and “Very much.” Items are scored from 1 to 5 and the individual item scores are summed to give a total domain score where high scores represent high impact of PBC on quality of life (Jacoby et al. 2005).	
 ▪ Change from baseline in PBC-40 for each of the 6 domain scores 	Change from baseline: observed PBC-40 score – baseline PBC-40 score for each of the 6 domains	Missing if baseline or observed value is missing.

Measure	Description	Variable	Derivation / Comment	Definition of Missing
Physician's Global Assessment of Disease Activity	
The Physician's Global Assessment of Disease Activity is the physician's assessment of the patient's overall disease activity due to PBC, as compared with all possible patients with PBC. The Physician's Global Assessment of Disease Activity is scored using a 100-mm visual analog scale (VAS), where 0 mm (measured from the left starting point of the line) indicates no disease activity and 100 mm (measured from the left starting point of the line) indicates the most severe disease activity possible for all patients with PBC. The Physician's Global Assessment of Disease Activity score is indicated by making a vertical tick mark on the line between 0 and 100 mm. There are benchmarks of 0 (0 mm), 1 (33 mm), 2 (67 mm), and 3 (100 mm) on the line corresponding to no, mild, moderate, and severe PBC disease activity, respectively.
	
 ▪ Change from baseline in Physician's Global Assessment of Disease Activity 	
Change from baseline: observed Physician's Global Assessment of Disease Activity score – baseline Physician's Global Assessment of Disease Activity score
	
Missing if baseline or observed value is missing.

Table JAIV.6.5. Description of Health Outcomes and Quality-of-Life Measures Analyses

Measure	Variable	Analysis Method (Section 6.1.3)	Population (Section 6.1.1)	Comparison/Time Point	Analysis Type
Itch Numeric Rating Scale (NRS)	• Change from baseline in itch	MMRM	mITT	Bari 4-mg and Bari 2-mg vs PBO; Week 12	Secondary analysis
		ANCOVA using LOCF	mITT	Bari 4-mg and Bari 2-mg vs PBO; Week 12	Supplementary analysis
Fatigue Numeric Rating Scale (NRS)	• Change from baseline in fatigue	MMRM	mITT	Bari 4-mg and Bari 2-mg vs PBO; Week 12	Secondary analysis
		ANCOVA using LOCF	mITT	Bari 4-mg and Bari 2-mg vs PBO; Week 12	Supplementary analysis
Functional Assessment of Chronic Illness Therapy Fatigue (FACIT-F)	• Change from baseline in FACIT-F total score	MMRM	mITT	Bari 4-mg and Bari 2-mg vs PBO; Week 12	Exploratory analysis
Quality of Life for Primary Biliary Cirrhosis (PBC-40)	• Change from baseline in PBC-40 domain scores	MMRM	mITT	Bari 4-mg and Bari 2-mg vs PBO; Week 12	Exploratory analysis
Physician's Global Assessment of Disease Activity	• Change from baseline in Physician's Global Assessment of Disease Activity	MMRM	mITT	Bari 4-mg and Bari 2-mg vs PBO; Week 12	Exploratory analysis

Abbreviations: ANCOVA = analysis of covariance; Bari = baricitinib; mITT = modified intent-to-treat; LOCF = last observation carried forward; MMRM = mixed model repeated measures; NRI = nonresponder imputation; PBO = placebo.

6.12. Bioanalytical and Pharmacokinetic/Pharmacodynamic Methods

Pharmacokinetic, Pharmacodynamic and Biomarker analyses to address exploratory objectives of this study will be described by Lilly in separate PK/PD and Biomarker analysis plans.

6.13. Safety Analyses

Analysis populations are defined in Section 6.1.1. Table JAIV.6.6 describes the analysis sets. “Analysis set” is a broad term used to define a set of definitions including the population, the treatment group(s), the time period(s), and the comparison(s) where applicable.

Table JAIV.6.6. Definition of Analysis Sets

Analysis Set	Analysis Population	Treatment Groups (Short Label)	Baseline Time Period	Postbaseline Time Period	Inferential Comparisons
Treatment (T)	Safety Population	Placebo, Bari 2 mg, Bari 4 mg	From screening to just before first study drug administration	From immediately after first dose of study drug to up to 30 days off drug follow-up time	When used: Bari 2 mg vs. placebo; Bari 4 mg vs. placebo
Treatment plus follow-up (T + FU)	Safety Population	Placebo, Bari 2 mg, Bari 4 mg	From screening to just before first study drug administration	From immediately after first dose of study drug to end of study participation.	When used: Bari 2 mg vs. placebo; Bari 4 mg vs. placebo

Abbreviation: Bari = baricitinib.

The planned safety analyses are consistent with compound-level safety standards, which are based on multiple sources, including company standards, internal and external subject matter experts, and cross-industry initiatives (e.g., white papers produced by a PhUSE Computational Science Working Group (a collaboration with FDA and PhUSE), published in the PhUSE Deliverables Catalog at <https://www.phuse.eu/white-papers>). Descriptions of the safety analyses are provided in this SAP; however, additional details (such as handling of unscheduled visits, missing data, etc.) are in compound-level safety standards.

The following statistical methods will be used for safety unless otherwise noted:

- The Fisher exact test will be used for treatment comparisons of proportions, and odds ratios with corresponding 95% confidence intervals will be presented where specified.
- Treatment differences in mean change for continuous measurements will be assessed using an analysis of covariance (ANCOVA) model fitting “baseline” as a covariate. Type 3 sums of squares will be used. In addition, the crude mean, standard deviation (SD), minimum, median, and maximum will be displayed.

Tests with two-sided p-values less than or equal to 0.05 will be referred to as having strong statistical evidence for a treatment difference, unless otherwise noted. However, p-values should not be over-interpreted, except for those associated with pre-specified hypotheses, since they correspond to data-driven hypotheses and hence are only useful as a flagging mechanism.

Additional safety analyses will be performed as part of the integrated safety analyses.

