10.1. Sample Size Determination

Approximately 20 patients will be randomized to the baricitinib 2-mg and placebo treatment groups for Cohort A. Twelve patients will be randomly assigned to the 2-mg treatment group and 8 patients to the placebo treatment group. This sample size is appropriate to provide sufficient preliminary safety and tolerability information for baricitinib 2-mg dose in patients with PBC prior to studying 4-mg baricitinib.

For Cohort B, 32 patients will be randomized to the baricitinib 4-mg and placebo treatment groups. Twenty patients will be randomized to the baricitinib 4-mg treatment group and 12 patients to placebo.

Overall, 20 patients per group will be assigned to the baricitinib 4-mg and placebo dose groups. Based on this sample size, this study will have approximately 81% power to detect a difference in ALP change from baseline between baricitinib 4-mg and placebo at Week 12 assuming that the true difference is 65 U/L. The sample size was determined based on a 2-sample t-test with 2-sided alpha level of 0.1 and a standard deviation of 80 U/L for the change from baseline in ALP. The sample size calculation was performed using nQuery® Advisor 7.0 software.

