6.1. General Considerations

This plan describes *a priori* statistical analyses for efficacy, health outcome, and safety that will be performed.

Statistical analysis of this study will be the responsibility of Eli Lilly and Company (Lilly) or its designee. The statistical analyses will be performed using SAS[®] Version 9.4 or a more recent version.

Not all displays described in this SAP will necessarily be included in the clinical study report (CSR). Not all displays will necessarily be created as a “static” display. Some may be incorporated into interactive display tools instead of or in addition to a static display. Any display described in this SAP and not included in the CSR would be available upon request.

Incidence rates and 95% confidence interval (CI) will be displayed for select safety endpoints.

Statistical tests of treatment effects and CIs will be performed at a 2-sided significance level of 0.1, unless otherwise stated. No multiplicity adjustment will be used in this study.

Data collected at early termination visits will be mapped to the next scheduled visit number for that patient if it falls within the visit window. For by-visit summaries, only visits in which a measure was scheduled to be collected will be summarized. Any unscheduled visit data will be included at the patient-level listings. However, the data will be included in other analyses, including shift analyses for safety analytes, change from baseline to endpoint using last observation carried forward (LOCF) analyses, and other categorical analyses.

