Treatment-emergent adverse event (TEAEs) are defined as AEs that first occurred or worsened in severity after the first dose of study treatment. The number of TEAEs as well as the number and percentage of patients who experienced at least 1 TEAE will be summarized using the Medical Dictionary for Regulatory Activities (MedDRA) for each system organ class (or a body system) and each preferred term by treatment group. SAEs and AEs that lead to discontinuation of investigational product and discontinuation from the study will also be summarized by treatment group. The Fisher exact test will be used to perform comparisons between the baricitinib and placebo groups.

All clinical laboratory results will be descriptively summarized by treatment group. Individual results that are outside of normal reference ranges will be flagged in data listings. Quantitative clinical hematology, chemistry, and urinalysis variables obtained at the baseline and postbaseline visits will be summarized as changes from baseline by treatment group and analyzed using analysis of covariance (ANCOVA) with treatment and baseline value in the model. The significance of within-treatment group changes from baseline will be evaluated by testing whether or not the treatment group least-squares mean (LSM) changes from baseline are different from zero; the p-value and standard error for the LSM change will be displayed. Differences in LSM will be displayed, with the p-value associated with the LSM comparison to placebo and a 95% CI on the LSM difference also provided. Treatment-emergent high/low for categorical laboratory safety analyses will also be produced. Categorical variables, including the incidence of abnormal values and incidence of AEs of special interest, will be summarized by frequency and percentage of patients in corresponding categories. Shift tables will be presented for selected measures.

Observed values and changes from baseline (predose or screening if predose is missing) for vital signs and physical characteristics will be descriptively summarized by treatment group and visit. Change from baseline to postbaseline in vital signs and body weight will be analyzed using ANCOVA with treatment and baseline value in the model.

The incidence and average duration of investigational product interruptions will be summarized and compared descriptively among treatment groups.

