6.16.1. Interim Analysis Plan

Analyses for the DMC will include listings and/or summaries of the following information:

- patient disposition, demographics, and baseline characteristics
- exposure
- timing of and reasons for study discontinuation and permanent study drug discontinuation
- adverse events (AEs), to include the following:
 - treatment-emergent AEs
 - serious AEs, including deaths
 - selected special safety topics
- clinical laboratory results
- vital signs

All listings will include patient ID and treatment group. Summaries will include TEAEs, SAEs, special topics AEs, and treatment-emergent high and low laboratory and vital signs in terms of counts, percentages and incidence rates where applicable. For continuous analyses, box plots of laboratory analytes will be provided by time point and summaries will include descriptive statistics such as mean, SD, minimum, 1st quartile, median, 3rd quartile, and maximum.

The DMC may request efficacy data if they feel there is value and to confirm a reasonable benefit/risk profile for ongoing patients in the study. If efficacy data are requested, change from baseline in ALP will be provided. Further details are given in the DMC charter.

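### For uncommon events (placebo rate about 5% or less) the Fisher p ≤ 0.05 safety flag usually misses a four- to six-fold excess, and no SAP event table names an interval for the difference from placebo

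*SAP*

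**What the plan says.** SAP section 6.13 sets the default for event-type safety data: "The Fisher exact test will be used for treatment comparisons of proportions", and "odds ratios with corresponding 95% confidence intervals will be presented where specified". It then fixes how a p-value is to be read: "Tests with two-sided p-values less than or equal to 0.05 will be referred to as having strong statistical evidence for a treatment difference". The next sentence cautions against over-interpretation. It says that p-values not tied to pre-specified hypotheses "hence are only useful as a flagging mechanism".

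Two other provisions concern intervals. SAP section 6.1 states: "Incidence rates and 95% confidence interval (CI) will be displayed for select safety endpoints". It does not name the endpoints. For continuous laboratory changes, SAP section 6.1.3 has "a 95% CI on the LSM difference also provided".

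Tables JAIV.6.7 to JAIV.6.19 list the event-type outputs: adverse events, hepatic and haematologic thresholds, infections, cardiovascular and thromboembolic events, malignancies and others. They plan counts, percentages, shift tables, listings and patient profiles. Herpes zoster also gets a rate adjusted for observation time. None of these tables names an odds ratio or a confidence interval.

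For Cohort A, SAP section 6.16.1 gives the DMC listings with treatment group, and event summaries "in terms of counts, percentages and incidence rates where applicable". Protocol section 10.1 says of the 12 versus 8 patients: "This sample size is appropriate to provide sufficient preliminary safety and tolerability information for baricitinib 2-mg dose".

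**The concern.** The Protocol (section 3.1) says that the trial's data are meant to inform benefit-risk in this disease, and the DMC review of Cohort A decides whether the 4-mg cohort opens. With arms of 12 to 20 patients, a Fisher test on an uncommon event can reach p ≤ 0.05 only when the imbalance is extreme. No flag is then the likely result even when a large relative excess is real.

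A between-arm interval would show how large an excess the data still allow. The SAP promises one for mean laboratory changes but ties none to any adverse event endpoint. The odds ratio it permits also works poorly here. With no placebo events, the sample odds ratio is infinite and has no finite upper limit. With no events in either arm, it cannot be estimated.

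**Working it through.** **Inputs from the documents.** 2 mg n = 12; 4 mg n = 20; placebo n = 8 + 12 = 20 (SAP 5.2). The cohorts are pooled, because SAP 6.1.1 puts both in the analysis populations and Table JAIV.6.6 has one placebo group. The flag is two-sided Fisher p ≤ 0.05.

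**Assumed inputs.** The documents give no event rate for this population, so placebo rates of 2%, 5%, 10% and 15% are illustrative. All randomised patients are taken to be in the safety population.

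**The plan's only power figure.** It is for ALP, 4 mg versus placebo. Noncentrality = 65 / (80 × √(1/20 + 1/20)) = 2.57, with 38 degrees of freedom and two-sided alpha 0.10. Power is 81.0%, which matches the stated 81%. No corresponding figure is given for any safety event.

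**What it takes to flag.** For x events against none at 20 versus 20, p = 2 × C(20,x)/C(40,x).
- x = 4: 2 × 4,845/91,390 = 0.106, not flagged.
- x = 5: 2 × 15,504/658,008 = 0.047, flagged.
- With one placebo event, 6 versus 1 gives p = 0.091 and 7 versus 1 gives p = 0.044.

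For 2 mg (12 versus 20), 3 versus 0 gives p = C(12,3)/C(32,3) = 220/4,960 = 0.044, and 4 versus 1 gives p = 0.053.

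**Chance of a flag.** Sum the binomial probabilities Bin(x; n₁, kπ) × Bin(y; 20, π) over every table with p ≤ 0.05 and the higher rate on baricitinib. Here π is the placebo rate and k the fold excess.

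| Placebo rate | 4 mg: 4-, 5-, 6-fold | 2 mg: 4-, 5-, 6-fold |
|---|---|---|
| 2% | 1%, 3%, 6% | 4%, 8%, 11% |
| 5% | 17%, 30%, 45% | 19%, 29%, 40% |
| 10% | 49%, 74%, 91% | 43%, 65%, 83% |
| 15% | 80%, 97%, >99% | 70%, 92%, >99% |

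In the 2% and 5% rows the miss rate runs from 100 − 45 = 55% to 100 − 1 = 99% for 4 mg, and from 100 − 40 = 60% to 100 − 4 = 96% for 2 mg. Loosening the flag to p ≤ 0.10 helps little. At a 5% placebo rate, a four-fold excess is then flagged 21% (4 mg) and 25% (2 mg) of the time.

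**What an interval would add.** The Newcombe interval for d = p₁ − p₀ combines the Wilson limits (l, u) of each arm: lower = d − √[(p₁ − l₁)² + (u₀ − p₀)²], upper = d + √[(u₁ − p₁)² + (p₀ − l₀)²].
- 6/20 versus 1/20: the Wilson limits are 0.145 to 0.519 and 0.009 to 0.236. Lower = 0.25 − √(0.1545² + 0.1861²) = 0.008; upper = 0.25 + √(0.219² + 0.041²) = 0.473. The difference is +25 points (+1 to +47), although Fisher does not flag it.
- 4/20 versus 0/20: +20 points, from just below 0 to +42. The odds ratio is infinite.
- 0/20 versus 0/20: upper limit 16 points. For 0/12 versus 0/20 it is 24 points. The odds ratio is not estimable in either.

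**Cohort A, per arm.** With no events in n patients, the one-sided 95% upper bound is 1 − 0.05^(1/n). For n = 12 this is 22%. A true 10% event rate leaves 12 patients event-free with probability 0.9¹² = 28%.

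**The case against.** **The result depends on the background rate.** A reader might infer that a four- to six-fold excess usually goes unflagged whatever the event. The documents give no rates, and the table shows that this fails at 10% for five- and six-fold excesses and at 15% for four-fold. The limit to rates of about 5% or less must stay attached.

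**Intervals may be specified elsewhere.** A reader might infer that the plan offers no bound at all. That goes too far. SAP 6.1 commits to intervals for some incidence rates, SAP 6.13 permits odds-ratio intervals, and fuller detail sits in compound-level safety standards that are not available here. What stands is narrower. The SAP itself names no event endpoint that carries an interval, and an interval on a single arm's rate does not bound a difference from placebo.

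**The SAP already restrains its p-values.** It treats them as flags and nowhere says that p > 0.05 means no difference. Listings, the eDISH plot, hepatic patient profiles, adjudication and medical review do not depend on p ≤ 0.05. Event counts by arm are planned, so a reader could compute an interval. All of this is correct and keeps the point modest. But case-level review does not show how large an excess remains possible, and the SAP says nothing about how to read an absent flag.

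**Cohort A.** A reader might infer that the DMC will judge Cohort A by Fisher p-values, or that the Protocol claims firm safety conclusions from it. Neither is supported. SAP 6.16.1 lists no test, it provides patient-level listings with treatment group, and Protocol 10.1 calls the information preliminary.

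**Small trials have low power.** This is true, and an interval does not change it. The interval makes the imprecision visible.

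**Conclusion.** The point holds as a reporting gap, not as an arithmetic error in the plan. For events with a placebo rate of about 5% or less, the planned flag misses a four- to six-fold excess in roughly 55% to 99% of trials for 4 mg and 60% to 96% for 2 mg. No event table in the SAP names an interval for the difference from placebo, and the one effect measure allowed breaks down when placebo has no events. The figures assume independent binomial counts, full enrolment, pooled placebo and illustrative event rates. The gap would narrow if the compound-level standards already assign between-arm intervals to named endpoints, which could not be checked. Because the SAP limits its p-values to flagging and plans extensive case review, this is a worthwhile low-cost improvement and not a threat to the trial's validity.

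**What to change.** 1. In SAP 6.13, replace the optional odds ratio with the risk difference, each dose minus placebo, and a Newcombe or Miettinen-Nurminen 95% interval. These are defined when a cell is zero. Apply it to adverse events of special interest, serious adverse events, discontinuations due to an adverse event, and the hepatic and haematologic threshold tables.
2. In the same section, state that p > 0.05 is not evidence of no difference. Fisher p-values can stay as descriptors.
3. In SAP 6.16.1, add exact per-arm upper bounds to the Cohort A tables for the DMC. For example, 0/12 events gives a one-sided 95% upper bound of 22%. This puts a number on the preliminary information that Protocol 10.1 and SAP 5.2 describe.

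The cost is SAP wording and a few columns in tables already planned, with no extra patients or data. The downside is wide intervals, which will make the safety tables look less reassuring.
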